#### CONFIDENTIAL

Compound No.: GKT137831 Sponsor: Genkyotex Author: Cmed Clinical Services

for such research. In such situations the research may be done only after consideration and approval of a research ethics committee.

#### **Use of Placebo**

33. The benefits, risks, burdens and effectiveness of a new intervention must be tested against those of the best proven intervention(s), except in the following circumstances:

Where no proven intervention exists, the use of placebo, or no intervention, is acceptable; or

Where for compelling and scientifically sound methodological reasons the use of any intervention less effective than the best proven one, the use of placebo, or no intervention is necessary to determine the efficacy or safety of an intervention

and the patients who receive any intervention less effective than the best proven one, placebo, or no intervention will not be subject to additional risks of serious or irreversible harm as a result of not receiving the best proven intervention.

Extreme care must be taken to avoid abuse of this option.

#### Post-Trial Provisions

34. In advance of a clinical trial, sponsors, researchers and host country governments should make provisions for post-trial access for all participants who still need an intervention identified as beneficial in the trial. This information must also be disclosed to participants during the informed consent process.

#### Research Registration and Publication and Dissemination of Results

35. Every research study involving human subjects must be registered in a publicly accessible database before recruitment of the first subject.

36. Researchers, authors, sponsors, editors and publishers all have ethical obligations with regard to the publication and dissemination of the results of research. Researchers have a duty to make publicly available the results of their research on human subjects and are accountable for the completeness and accuracy of their reports. All parties should adhere to accepted guidelines for ethical reporting. Negative and inconclusive as well as positive results must be published or otherwise made

publicly available. Sources of funding, institutional affiliations and conflicts of interest must be declared in the publication. Reports of research not in accordance with the principles of this Declaration should not be accepted for publication.

#### Unproven Interventions in Clinical Practice

37. In the treatment of an individual patient, where proven interventions do not exist or other known interventions have been ineffective, the physician, after seeking expert advice, with informed consent from the patient or a legally authorised representative, may use an unproven intervention if in the physician's judgement it offers hope of saving life, re-establishing health or alleviating suffering. This intervention should subsequently be made the object of research, designed to evaluate its safety and efficacy. In all cases, new information must be recorded and, where appropriate, made publicly available.

World Medical Association, Inc. - All Rights reserved.
Asociación médica mundial - Todos los derechos reservados.
L'Association Médicale Mondiale - Tous droits réservés.

## APPENDIX D: PRURITUS VAS

Guidance on completing the pruritus VAS:

- Write the number between 0 and 10 underneath the scale which best represents the intensity of your itch over the last 24 hours. Do not include a decimal.
- A score of 0 = no itch; a score of 10 = maximum itch, i.e., severe, continuous, day and night intolerable itch.
- Do not mark a cross on the actual line.

Score in the last 24 hours: \_\_\_\_\_\_ (write the number from 0 to 10 which best represents the intensity of your itch, with no decimal).

## APPENDIX E: PBC-40 QUESTIONNAIRE

Protocol No.: GSN000300 Protocol Version No.: Final 4.0; Amendment 3 Protocol Date: 24 July 2018 Compound No.: GKT137831 Sponsor: Genkyotex Author: Cmed Clinical Services

P	a	ti	e	n	t	Ι	D

For each statement, please circle the response that comes closest to how you feel. If any of the statements do not apply to you please circle 'does not apply'.

Can you say how often the following statements about digestion and diet applied to you IN THE LAST FOUR WEEKS?

1	I was able to eat what I liked	Never	Rarely	Sometimes	Most of the time	Always	
2	I ate or drank only a small amount, and still felt bloated	Never	Rarely	Sometimes	Most of the time	Always	Did not
3	I felt unwell when I drank alcohol	Never	Rarely	Sometimes	Most of the time	Always	apply /never drink alcohol

And IN THE LAST FOUR WEEKS, how often did you experience any of the following?

4	I had discomfort in my right side	Never	Rarely	Sometimes	Most of the time	Always
5	I had dry eyes	Never	Rarely	Sometimes	Most of the time	Always
6	My mouth was very dry	Never	Rarely	Sometimes	Most of the time	Always
7	I had aches in the long bones of my arms and legs	Never	Rarely	Sometimes	Most of the time	Always

Some people with PBC experience itching. How often did you experience itching IN THE LAST FOUR WEEKS? If you did not itch, please circle 'does not apply'

8	Itching disturbed my sleep	Never	Rarely	Sometimes	Most of the time	Always	Did not apply/ no itch
9	I scratched so much I made my skin raw	Never	Rarely	Sometimes	Most of the time	Always	Did not apply/no itch
10	I felt embarrassed because of the itching	Never	Rarely	Sometimes	Most of the time	Always	Did not apply/no itch
## Fatigue can also be a problem for many people with PBC. How often did the following statements apply to you IN THE LAST FOUR WEEKS?

11	I had to force myself to get out of bed	Never	Rarely	Sometimes	Most of the time	Always
12	I had to have a sleep during the day	Never	Rarely	Sometimes	Most of the time	Always
13	Fatigue interfered with my daily routine	Never	Rarely	Sometimes	Most of the time	Always
14	I felt worn out	Never	Rarely	Sometimes	Most of the time	Always
15	I felt so tired, I had to force myself to do the things I needed to do	Never	Rarely	Sometimes	Most of the time	Always
16	I felt so tired, I had to go to bed early	Never	Rarely	Sometimes	Most of the time	Always
17	Fatigue just suddenly hit me	Never	Rarely	Sometimes	Most of the time	Always
18	PBC drained every ounce of energy out of me	Never	Rarely	Sometimes	Most of the time	Always

## The next section is about the effort and planning that can be involved in living with PBC. Thinking about THE LAST FOUR WEEKS, how often did the following statements apply to you?

19	Some days it took me a long time to do anything	Never	Rarely	Sometimes	Most of the time	Always
20	If I was busy one day I needed at least another day to recover	Never	Rarely	Sometimes	Most of the time	Always
21	I had to pace myself for day-to-day things	Never	Rarely	Sometimes	Most of the time	Always

The following statements are about the effects that PBC may have on things like memory and concentration. Thinking about THE LAST FOUR WEEKS, how often did the following statements apply to you?

22	Because of PBC I had to make a lot of effort to remember things	Never	Rarely	Sometimes	Most of the time	Always
23	Because of PBC I had difficulty remembering things from one day to the next	Never	Rarely	Sometimes	Most of the time	Always
24	My concentration span was short because of PBC	Never	Rarely	Sometimes	Most of the time	Always

25	Because of PBC, I had difficulty keeping up with conversations	Never	Rarely	Sometimes	Most of the time	Always
26	Because of PBC, I found it difficult to concentrate on anything	Never	Rarely	Sometimes	Most of the time	Always
27	Because of PBC, I found it difficult to remember what I wanted to do	Never	Rarely	Sometimes	Most of the time	Always

Now some more general statements about how PBC may be affecting you as a person. How much do the following statements apply to you?

28	Because of PBC, I get more stressed about things than I used to	Not at all	A little	Somewhat	Quite a bit	Very much	
29	My sex life has been affected because of PBC	Not at all	A little	Somewhat	Quite a bit	Very much	Does not apply
30	Having PBC gets me down	Not at all	A little	Somewhat	Quite a bit	Very much	
31	I feel I neglect my family because of having PBC	Not at all	A little	Somewhat	Quite a bit	Very much	Does not apply
32	I feel guilty that I can't do what I used to do because of having PBC	Not at all	A little	Somewhat	Quite a bit	Very much	
33	I worry about how my PBC will be in the future	Not at all	A little	Somewhat	Quite a bit	Very much	

These statements relate to the possible effects of PBC on your social life. Thinking of your own situation, how much do you agree or disagree with them?

34	I sometimes feel frustrated that I can't go out and enjoy myself	Strongly agree	Agree	Neither agree nor disagree	Disagree	Strongly disagree
35	I tend to keep the fact that I have PBC to myself	Strongly agree	Agree	Neither agree nor disagree	Disagree	Strongly disagree
36	I can't plan holidays because of having PBC	Strongly agree	Agree	Neither agree nor disagree	Disagree	Strongly disagree
37	My social life has almost stopped	Strongly agree	Agree	Neither agree nor disagree	Disagree	Strongly disagree

3

## The next section is about the impact that PBC may be having on your life overall. How much do you agree or disagree with the following statements?

38	Everything in my life is affected by PBC	Strongly agree	Agree	Neither agree nor disagree	Disagree	Strongly disagree
39	PBC has reduced the quality of my life	Strongly agree	Agree	Neither agree nor disagree	Disagree	Strongly disagree
40	I can still lead a normal life, despite having PBC	Strongly agree	Agree	Neither agree nor disagree	Disagree	Strongly disagree

The next few questions are about your general health and well being:							
A	In general, would you say your health is:	Excellent	Very good	Good	Fair	Poor	
в	And how would you have rated it before you had PBC?	Excellent	Very good	Good	Fair	Poor	
с	COMPARED TO ONE YEAR AGO, how would you rate your health in general now?	Much better	Somewhat better	About the same	Somewhat worse	Much worse	

THANK YOU FOR TAKING THE TIME TO COMPLETE

4

## APPENDIX F: CLOSE OBSERVATION PROCEDURES

- 1. Interrupt the investigational agent administration
- 2. Repeat liver biochemistries and additional testing within 24-72 hours
- 3. Monitor patient twice or thrice a week until liver biochemistries (ALT, AST, alkaline phosphatase, total bilirubin, and coagulation profile [INR]) resolve, stabilize or return to within baseline values
- 4. Monitor liver biochemistries once a week if abnormalities stabilize and the patient is asymptomatic
- 5. Obtain a detailed history for symptoms assessment: appearance or worsening of clinical symptoms of hepatitis (fatigue, nausea, vomiting, right upper quadrant pain or tenderness, fever, rash or eosinophilia). If a patient is symptomatic, the drug must be discontinued immediately and a potential DILI evaluation must be performed.
- 6. Obtain a more detailed history of symptoms and prior or concomitant diseases;
- 7. Obtain a history for concomitant medications, acetaminophen, dietary supplements, herbal remedies, other over the counter medications, recreational drug use, and special diets
- 8. If possible quantify the alcohol consumption to assess for alcoholic hepatitis
- 9. Obtain a history of exposure to environmental chemical agents.
- 10. If INR is also elevated, a trial of intravenous vitamin K administration may be considered, especially in cholestatic patients.

Follow-Up Procedures for patient(s) who meet *potential DILI evaluation criteria*:

- 1. Viral hepatitis serology including:
  - a. Hepatitis A IgM antibody;
  - b. Hepatitis B surface antigen and Hepatitis B Core Antibody (IgM);
  - c. Hepatitis C RNA;
  - d. Hepatitis E IgM antibody.
  - e. Cytomegalovirus IgM antibody;
  - f. Epstein-Barr viral capsid antigen IgM antibody (or if unavailable, obtain heterophile antibody or monospot testing); however IgM antibodies must be sent out asap
  - g. Blood sample for pharmacokinetic (PK) analysis, obtained within 12 hours of last dose. Record the date/time of the PK blood sample draw and the date/time of the last dose of study treatment prior to blood sample draw on the CRF. If the date or time of the last dose is unclear, provide the participant's best approximation.
  - h. Serum Creatine phosphokinase (CPK) and lactate dehydrogenase (LDH).
  - i. Fractionate bilirubin, if total bilirubin >2xULN
  - j. Assess for peripheral eosinophilia
  - k. Assess for hypoxic/ischemic hepatopathy; and biliary tract disease

The following are required for patients who meet the stopping criteria for both ALT and total bilirubin OR experiences clinical symptoms of hepatitis:

1. Anti-nuclear antibody, anti-smooth muscle antibody, Type 1 anti-liver kidney microsomal antibodies and quantitative total immunoglobulin G (IgG or gamma globulins).

Protocol No.: GSN000300	Compound No.: GKT137831
Protocol Version No.: Final 4.0; Amendment 3	Sponsor: Genkyotex
Protocol Date: 24 July 2018	Author: Cmed Clinical Services

- 2. If required evaluation of competing undiagnosed liver disease (hemochromatosis, Wilson's disease, alpha-1 anti-trypsin deficiency)
- 3. Serum acetaminophen levels OR serum acetaminophen adducts by HPLC assay (quantifies potential acetaminophen contribution to liver injury in participants with definite or likely acetaminophen use in the preceding week).
- 4. Liver imaging (ultrasound, magnetic resonance, or computerized tomography) to evaluate liver disease.
- 5. A Liver Biopsy

Treatment with investigational agent could be re-initiated if these abnormalities stabilize, return to pre-trial baseline or normalize and a causative agent was found.

Investigational agent must be discontinued and patient must be followed until the clinical and laboratory abnormalities stabilize or normalize if the following criteria are met:

- 1. If close monitoring of a patient is not possible.
- 2. In presence of total bilirubin elevation (>2 x ULN or >1.5 x baseline); with any degree of aminotransferase elevation; AND if there is appearance of symptoms i.e., fatigue, nausea, vomiting, right upper quadrant pain or tenderness, fever, rash, and/or eosinophilia (>5%).
- 3. If any degree of total bilirubin, ALT, or AST elevation recurs following re-challenge with study drug.

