# 5.3 Exclusion Criteria

A potential subject who meets any of the following criteria will be excluded from participation in this study:

- 1. A positive pregnancy test or breast-feeding for female subjects.
- 2. Any hepatic decompensation, defined as a past or current history of hepatic encephalopathy, gastrointestinal tract bleeding due to esophageal varices, or ascites.
- 3. INR > 1.2 unless subject is on anticoagulant therapy.
- 4. ALT > 3 x ULN.
- 5. Total bilirubin > 1 x ULN.
- 6. Planned or current plasmapheresis or other extra-corporeal treatments (e.g., MARS) for treatment-refractory pruritus.
- History of liver transplantation, current placement on a liver transplant list or current MELD score
  ≥ 15.
- 8. Cirrhosis with complications, including history or presence of: spontaneous bacterial peritonitis, hepatocellular carcinoma.
- 9. Hepatorenal syndrome (type I or II) or Screening serum creatinine > ULN.
- 10. Competing etiology for liver disease (e.g., hepatitis C, active hepatitis B, NASH, ALD, autoimmune hepatitis, primary sclerosing cholangitis, Gilbert's Syndrome).
- 11. Subjects receiving prohibited medications within 3 months of Screening (Visit 1) according to the list (a, b and c) provided in Section 6.6.2.
- 12. Treatment with any investigational agent within 4 weeks of Screening (Visit 1) or 5 half-lives of the IMP (whichever is longer).
- 13. A history of long QT syndrome.
- 14. Evidence of any of the following cardiac conduction abnormalities during the screening period:
  - A QTc Fredericia interval > 450 milliseconds for males and > 470 milliseconds for females.
  - A second or third degree atrioventricular block not successfully treated with a pacemaker.
- 15. A history of severe cardiovascular disease defined as any of the following within the 12 weeks preceding initiation of study treatment:
  - Acute myocardial infarction or unstable angina pectoris.

- A coronary revascularization procedure.
- Congestive heart failure New York Health Association (NYHA) Class III or IV.
- Stroke, including a transient ischemic attack.
- 16. History of cancer in the preceding 5 years, except adequately treated non-melanoma skin cancer, carcinoma *in situ* of the cervix, *in situ* prostate cancer, *in situ* breast ductal carcinoma, or superficial bladder cancer stage 0).
- 17. The occurrence of any acute infection requiring systemic antibiotic therapy within 2 weeks prior to Screening (Visit 1), or HIV infection.

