# 6.3.1 In case of Confirmed or Suspected Drug Induced Liver Injury

In case of any of the following events:

- Grade ≥ 2 severity liver-related AE, or
- Grade ≥ 3\_severity ALT or AST (i.e. ≥ 5x ULN), or
- Grade ≥ 2 severity total bilirubin (i.e. ≥ 1.5x ULN), or
- Grade  $\geq$  2 severity INR (i.e.  $\geq$  1.5x ULN)

The investigator will instruct the subject to interrupt IMP administration and to return to the study center within 2-3 days to perform a re-test and to undergo additional investigations (i.e. close monitoring as described in Appendix F) to assess for potential DILI. In case of confirmed or suspected DILI as assessed by the investigator, IMP administration must be permanently discontinued, in particular in the following cases:

• Re-test ALT and/or AST values ≥ 3 x baseline and greater than the ULN associated with new onset total bilirubin ≥ 2 x ULN or INR ≥ 1.5.

If subjects live in a remote area, they can be tested locally and the results communicated to the investigator site promptly.

In case of non-confirmed DILI, IMP administration will be resumed in accordance with the protocol and subject will remain under close monitoring as deemed necessary by the investigator.

Any confirmed or suspected DILI event will be closely monitored by the investigator and reported to Sponsor following the same procedure as for SAEs, as described in Section 9.5.

Withdrawals will be handled as described in Section 5.6.5.

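### Section 6.3.1 and Appendix F can lead to different decisions on resuming or stopping study drug after the same liver signal, and no precedence is stated

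*Protocol*

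**What the plan says.** **Section 6.3.1.** Drug is interrupted and the subject re-tested for any of four signals:

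- a liver-related AE of Grade 2 or above;
- Grade 3 or above "ALT or AST (i.e. ≥ 5x ULN");
- Grade 2 or above "severity total bilirubin (i.e. ≥ 1.5x ULN");
- INR at or above 1.5 x ULN.

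The site is then sent to "close monitoring as described in Appendix F". Confirmed or suspected DILI, in the investigator's judgement, means a permanent stop. The case singled out is a re-test ALT or AST at least 3 x baseline and above ULN, with new-onset bilirubin of at least 2 x ULN or INR of at least 1.5. Otherwise, "In case of non-confirmed DILI, IMP administration will be resumed in accordance with the protocol".

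**Appendix F.** After the extended work-up list, for subjects who meet both the ALT and bilirubin stopping criteria or have hepatitis symptoms, it says: "Treatment with investigational agent could be re-initiated if these abnormalities stabilize, return to pre-trial baseline or normalize and a causative agent was found". It then lists when drug must be discontinued. Item 1 is that close monitoring is not possible. Item 2 begins "In presence of total bilirubin elevation (>2 x ULN or >1.5 x baseline); with any degree of aminotransferase elevation" and also requires that symptoms appear, fatigue among them. Item 3 is "If any degree of total bilirubin, ALT, or AST elevation recurs following re-challenge with study drug".

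**Related text.** The mandatory withdrawal list in Section 5.6.4 refers to Section 6.3.1 alone for DILI. Section 9.5 uses discontinuation for a pause that lasts until re-testing. Section 5.3 excludes ALT above 3 x ULN and "Total bilirubin > 1 x ULN", and lists no AST limit. Section 2.1.3.3 expects aminotransferases to be modestly raised in PBC.

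**The concern.** Both passages are current and apply after the same event. Section 6.3.1 sends the site to Appendix F for monitoring, and the appendix goes further by setting its own conditions for restarting and stopping drug. Where those differ from Section 6.3.1, a site has nothing in the protocol to tell it which to follow.

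Section 2.3 explains why this matters. The trial tests a higher dose for longer, accumulation in liver tissue is expected, and Section 6.3.1 is the named safeguard against DILI. Two sites that each follow the protocol could stop or resume drug differently for the same subject. Counts of DILI-related discontinuation by dose would then depend partly on which page was followed. So could the unscheduled safety board meetings that Section 9.7 attaches to a permanent interruption for DILI.

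**Working it through.** The plan gives no figure to reproduce. The check puts the limits on one scale and then applies both sets of rules to hypothetical subjects. All values are in multiples of ULN, and the subject values are assumptions with baselines inside the Section 5.3 limits.

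**Bilirubin limits.** Let b be baseline bilirubin. Appendix F's relative limit is 1.5 × b.

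- Entry allows b up to 1, so the limit is at most 1.5 × 1 = 1.5. That is below Appendix F's own absolute limit of 2 and never above the Section 6.3.1 trigger of 1.5.
- The limit lies inside the normal range when 1.5 × b < 1, that is b < 1/1.5 = 0.67. Examples: b = 0.4 gives 0.60, b = 0.5 gives 0.75, b = 0.6 gives 0.90. By contrast, b = 0.8 gives 1.20.
- The absolute limit of 2 comes first only if 1.5 × b > 2, that is b > 1.33.

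**Aminotransferase limits.** The case singled out in Section 6.3.1 needs 3 × baseline: 4.5 for a baseline of 1.5, 6.0 for 2.0 and 7.5 for 2.5. Item 3 of Appendix F has no number. If elevation means above ULN, every ALT above 1 and up to the entry maximum of 3 counts.

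**Side by side.**

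| Subject | Section 6.3.1 | Appendix F |
|---|---|---|
| A. No symptoms; re-test ALT 6 (baseline 1.5, limit 4.5); bilirubin 2.2 (baseline 0.6); another cause found; values settle | Permanent stop | Could be re-initiated |
| B. ALT 5.5 (baseline 2.5); bilirubin 0.8; DILI not confirmed; no cause found; values settle | Resumed | Re-initiation condition not met, if it covers all subjects |
| C. After resumption, ALT at its own baseline of 2.0; bilirubin 0.6 | No trigger | Discontinue under item 3, if elevation means above ULN |
| D. ALT 2 (baseline 2); bilirubin 0.9 (baseline 0.5, limit 0.75); new mild fatigue, not a Grade 2 liver-related AE | No trigger | Discontinue under item 2 |
| E. ALT 9 (baseline 2, limit 6); bilirubin 2.5; symptoms | Permanent stop | Discontinue |
| F. As B, but a cause is found | Resumed | Could be re-initiated |

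A and B show that the scope of the re-initiation sentence does not settle the matter. If it covers every subject, B conflicts. If it covers only the group named just above it, B drops out. A remains, because that group includes subjects for whom Section 6.3.1 requires a permanent stop.

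D bears most directly on a subject already under close observation, since that is how Section 6.3.1 brings a site to Appendix F.

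**The case against.** The best case for the current text is that Section 6.3.1 governs. Section 5.6.4 cites only that section, and Appendix F is called for monitoring. The re-initiation sentence is permissive and may apply only to the group above it. Investigator judgement can also bring the passages together. With no cause found, DILI may still be suspected and drug stopped, which removes B. With another cause found, DILI may no longer be suspected and drug resumed, which removes A. Resuming as the protocol directs could also be read to include Appendix F.

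On item 3, Appendix F elsewhere treats a return to baseline as resolution, so a value back at baseline may not be a recurrence. On item 2, symptoms must appear, so long-standing PBC fatigue does not obviously count.

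Much of this stands as a limit on the point. Each is a possible reading, but none is written down, and they do not all point the same way.

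Several stronger conclusions that a reader might draw are not supported:

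- **The passages contradict each other throughout.** They agree in E and F.
- **Entry values alone meet Appendix F's limits.** Item 2 also needs a bilirubin rise and symptoms, and item 3 needs a re-challenge.
- **Section 6.3.1 prompts no re-test below an ALT of 5 x ULN.** Bilirubin, INR or a liver-related AE can prompt one at any ALT.
- **The 2 x ULN bilirubin limit can never act.** Section 7.2 does not require every eligibility test to be repeated on Day 1, so a Day 1 baseline above 1.33 x ULN is possible.

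**Conclusion.** The point holds in a limited form: the two passages can give different outcomes for definable subjects, and the protocol does not say which prevails.

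- **Resumption.** They differ on whether a cause must be found. On the narrower reading of Appendix F, it permits re-initiation where Section 6.3.1 requires a permanent stop.
- **After re-challenge.** Item 3 has no counterpart in Section 6.3.1 and no reference level. Read against ULN, a return to an ALT that entry allows can meet it.
- **Bilirubin with symptoms.** Item 2 can require discontinuation where Section 6.3.1 has no trigger. For baselines up to 1 x ULN its relative limit is always reached before 2 x ULN, and below 0.67 x ULN it can be crossed within the normal range.

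Appendix F also leaves open whether its discontinuation is permanent.

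This rests on the text as written and on hypothetical subjects. Case C assumes elevation is judged against ULN, and D assumes the fatigue is new and not graded 2 or above as a liver-related AE. The documents give no basis for estimating how often such cases would arise. Because this is a participant-safety rule that sites could follow faithfully and still apply differently, it should be corrected and not left to interpretation.

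**What to change.** Reconcile Sections 5.6.4, 6.3.1, 9.5 and Appendix F into one set of conditions for interruption, resumption and permanent discontinuation, or state which passage governs where they differ. Within that:

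- say which subjects the re-initiation sentence covers;
- give the reference, x ULN or x baseline, for each elevation, taking account of the liver values that Section 5.3 admits;
- say wherever discontinuation is required whether it is temporary or permanent.

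The choice of thresholds and clinical rules belongs to the sponsor and its advisers.

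The cost is protocol amendment wording and its approval, which under Section 12.1 means ethics committee approval and, where applicable, regulatory approval. No visits or tests are added.
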